Radiation will begin within 14 days of the planning MRI (obtained with standard gadolinium). All patients will receive either AGuIX (100mg/kg) or placebo (normal saline, as discussed below) injection 2-5 days before radiation initiation in order to infuse the core of the tumor with AGuIX in those assigned to receive it. A brain MRI will be performed on this date, both pre-infusion and post-infusion. For patients receiving stereotactic radiosurgery (SRS, focused radiation in 1 day) alone the next AGuIX (100mg/kg) or placebo injection will take place 1-5 hours (preferably 2 hours) before the radiation treatment; no further AGuIX / placebo injections will be given. For patients managed with stereotactic radiotherapy (SRT, focused radiation in 5 days) with or without SRS AGuIX (100mg/kg) or placebo injection will be given 1-5 hours (preferably 2 hours) before radiation treatment on day 1 of radiation and 1-5 hours (preferably 2 hours) before radiation on day 3 of radiation. Patients receiving both SRS and SRT can receive treatment over 5 or 6 days, as discussed below. In both cases, SRS should be performed on day 1; SRT would start on day 1 or day 2, respectively.

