7.6 Routine Adverse Event Reporting

All Adverse Events **must** be reported in routine study data submissions to the study PI on the toxicity case report forms. **AEs reported through expedited processes (e.g., reported to the IRB, FDA, etc.) must also be reported in routine study data submissions.**

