
The length of follow up for the neurocognitive secondary endpoint will also be 12 months. The length of follow up for all other endpoints will be until censoring or death. Of note, the usual clinical care for patients with brain metastases involves a radiation oncology visit, history, and an MRI brain every 1.5-3 months until death or other loss to follow up. All secondary endpoints (with the exception of neurocognition and health status) are assessed as part of usual clinical care. Patients can elect to follow-up with a local provider following the completion of radiation if deemed appropriate by the study PI, in which case brain imaging must be retrieved and digitally stored. Providers will call patients whom elect to follow-up with a local provider to discuss imaging results and complete study documentation; in such cases quality of life testing and neurocognition do not need to be pursued.

Study calendars are presented here:

Patients managed with SRS

	Baseline ^a	Radiation Planning	2-5 Days Before Radiation Initiation	Radiation Day 1 ^b	Follow Up ^c	eDC Timepoints
Informed consent	X					
Medical history	X				X	Baseline
Karnofsky performance status	X				X	Baseline, Follow-up
CT simulation		X				Pre-Radiation
MRI brain			X ^d		X	Pre-Radiation, Follow-up
SRS				X		Radiation
AGuIX or placebo administration			X	X		Pre-Radiation, Radiation
Quality of life assessment	X				X	Baseline, Follow-up
Health status assessment	X				X	Baseline, Follow-up
Neurocognitive Assessment	X				X ^e	Baseline, Follow-up
Volumetric imaging	X				X	Baseline, Follow-up
AE assessment ^f	X		X ^g	X ^g	X	Baseline, Pre-Radiation, Radiation, Follow-up

Abbreviations: AE=Adverse Event; AGuIX=Activation and Guidance of Irradiation by X-ray; CT=Computed Tomography; MRI=Magnetic Resonance Imaging; SRS=Stereotactic Radiosurgery; SRT=Stereotactic Radiotherapy

a. Within 21 days

b. Within 14 days of radiation planning MRI

c. Follow up visits occur post radiation at approximately 1.5/3/5/7/9 months, and every 3 months thereafter (+/- 4 weeks except 1.5 month visit which is +/- 1 week)

d. To be performed before and after administration of AGuIX vs placebo

e. Neurocognitive assessments occur in the follow up period at 3 months and 12 months

f. For the purpose of this protocol, acute adverse events collected and documented on CRFs are only acute non-hematologic grade 3 or higher toxicities that did not predate radiation and are possibly, probably or definitely related to radiation/AGuIX

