g. Adverse effects on days that AGuIX is administered will be assessed prior to administration of AGuIX

Patients managed with SRT (including those managed with SRS and SRT over 5 days)

	Baseline ^a	Radiation Planning	2-5 Days Before Radiation Initiation	Radiation Day 1 ^b	Radiation Day 2	Radiation Day 3	Radiation Day 4	Radiation Day 5	Follow Up ^c	eDC Timpoints
Informed consent	X									
Medical history	X									Baseline
Karnofsky performance status	X								X	Baseline, Follow-up
MRI brain			X ^d						X	Pre-Radiation, Follow-up
CT simulation		X								Baseline, Follow-up
SRS				X ^e						Radiation
SRT				X	X	X	X	X		Radiation
AGuIX or placebo administration			X	X		X				Pre-Radiation, Radiation
Quality of life assessment	X								X	Baseline, Follow-up
Health status assessment	X								X	Baseline, Follow-up
Neurocognitive Assessment	X								X ^f	Baseline, Follow-up
Volumetric imaging	X								X	Baseline, Follow-up
AE assessment ^g	X		X ^h	X ^h					X	Baseline, Pre-Radiation, Radiation, Follow-up

Abbreviations: AE=Adverse Event; AGuIX=Activation and Guidance of Irradiation by X-ray; CT=Computed Tomography; MRI=Magnetic Resonance Imaging; SRS=Stereotactic Radiosurgery; SRT=Stereotactic Radiotherapy

a. Within 21 days

b. Within 14 days of radiation planning MRI

c. Follow up visits occur post radiation at approximately 1.5/3/5/7/9 months, and every 3 months thereafter (+/- 4 weeks except 1.5 month visit which is +/- 1 week) d. To be performed before and after administration of AGuIX vs placebo

e. If indicated

f. Neurocognitive assessments occur in the follow up period at 3 months and 12 months

g. For the purpose of this protocol, acute adverse events collected and documented on CRFs are only acute non-hematologic grade 3 or higher toxicities that did not predate radiation and are possibly, probably or definitely related to radiation/AGuIX

h. Adverse effects on days that AGuIX is administered will be assessed prior to administration of AGuIX

Patients managed with SRS and SRT over 6 days:

	Baseline ^a	Radiation Planning	2-5 Days Before Radiation Initiation	Radiation Day 1 ^b	Radiation Day 2	Radiation Day 3	Radiation Day 4-6	Follow Up	eDC Timepoints
Informed consent	X								
Medical history	X								Baseline
Karnofsky performance status	X							X	Baseline, Follow-up
MRI brain			X ^d					X	Pre-Radiation, Follow-up
CT simulation		X							Baseline
SRS				X					Radiation
SRT					X	X	X		Radiation

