In addition, we utilize a second early stopping rule applicable to the entire cohort. If two or more of the first six patients randomized to receive AGuIX display an acute, grade 3-5 non-hematologic toxicity within 1.5 months of the end of protocol-based treatment that is possibly, probably, or definitely related to AGuIX administration the study will be closed to further enrollment. If the true rate of such toxicity is 33%, then there is a 65% chance that at least two of the first six patients would experience it. If this early stopping rule is met, then any plans to re-open the study with a modified treatment plan will need to be formally reviewed and approved by the sponsor and by the DF/HCC SRC/IRB prior to activation. If there are less than two instances of acute, grade 3-5, non-hematologic toxicity within 1.5 months of the end of protocol-based treatment that are possibly, probably, or definitely related to AGuIX administration among the first six patients, the study will proceed to full accrual. Of note the first post-treatment assessment will occur at 1.5 months. Case report forms for such patients will be monitored weekly by the unblinded CRC until either the early stopping rule is met or it is determined that the early stopping rule cannot be met.

The study will incorporate an early stopping rule for futility. After 50% of the total patient accrual (that is, 67 of the 134 patients) have been observed through 9 months, we will evaluate the best intracranial response rate (iRR) achieved over 9 months for the pre-specified futility analysis. It is expected that the control iRR rate is on the order of 70% and the experimental iRR rate will be improved to at least 86%. Under this scenario, the overall study has 83% power for this comparison at full information (98 intracranial responses) using a one-sided 0.10 level test of proportions. For 50% information time on iRR (49 intracranial responses), it is projected that this will be reached roughly at study month 26, given an expected accrual of 47-48 patients per year, 17 months of accrual and 9 months follow-up for the first 67 patients. The Wieand rule will be used to assess futility. If the iRR is higher the experimental arm the study will proceed to full accrual. If the iRR is high in the non-experimental/placebo arm we will examine local control on

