13.7. Reporting and Exclusions

13.7.1. Evaluation of Toxicity

All participants will be evaluable for toxicity from the time of their first treatment.

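### The calendar footnote ties recording of acute toxicity to radiation, not to the first AGuIX/placebo injection, so it contradicts the stopping rule that depends on those records

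*Protocol*

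**What the plan says.** **What is recorded.** In Protocol section 10, footnote f of the SRS and 6-day calendars and footnote g of the 5-day SRT calendar say which acute adverse events go on the case report forms (CRFs): "only acute non-hematologic grade 3 or higher toxicities that did not predate radiation", with at least a possible relation to radiation or AGuIX.

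**When the agent is given.** Section 5.1 gives all patients an AGuIX or placebo "injection 2-5 days before radiation initiation". For SRS alone, the second injection comes "1-5 hours (preferably 2 hours) before the radiation treatment". The SRT schedules use the same 1 to 5 hour lead on radiation days 1 and 3.

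**What the stopping rule counts.** Section 13.4 closes the whole study to enrollment on this trigger: "If two or more of the first six patients randomized to receive AGuIX display an acute, grade 3-5 non-hematologic toxicity within 1.5 months". The window is measured from completion of protocol treatment, and the toxicity must be at least possibly related to AGuIX administration. CRFs for these patients are checked weekly by the unblinded coordinator. The protocol quotes a 65% chance of meeting the criterion at a true rate of 33%.

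**What other sections say.** Section 7.6 requires that all adverse events "be reported in routine study data submissions to the study PI on the toxicity case report forms". Section 7.3.2 sends any adverse event after the initial dose, up to 30 days after the last, to the study PI. Section 13.7.1 states: "All participants will be evaluable for toxicity from the time of their first treatment".

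**When adverse events are checked.** Another footnote (g, or h in the 5-day SRT calendar) states: "Adverse effects on days that AGuIX is administered will be assessed prior to administration of AGuIX". The adverse-event row is marked at baseline, at the visit 2 to 5 days before radiation, on radiation day 1 and at follow-up.

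**The concern.** The footnote's filters on grade and hematologic type match those of the stopping rule, and its relatedness filter is no narrower. The filter on onset has no counterpart in the rule. Because treatment with AGuIX starts days before radiation, a reaction to the first injection can both satisfy the rule and fail the footnote. The same holds for a reaction in the hours between the day-1 injection and the beam.

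At stake is a safety rule based on only six AGuIX patients, where one unrecorded patient can decide the outcome. Section 7.1 notes that few patients have received AGuIX and lists, by analogy with a gadolinium salt, hypersensitivity and anaphylactic reactions. If such a reaction occurred, it could follow the first exposure, which is the exposure the footnote leaves out.

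**Working it through.** **1. The passages side by side.** Take an AGuIX-related grade 3 or higher non-hematologic event that begins after the first injection and before the first radiation treatment.

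| Protocol section | Is the event recorded or counted? |
|---|---|
| 10, footnote f/g | No: onset is before radiation |
| 13.4, whole-cohort rule | Yes: no radiation anchor |
| 7.6 | Yes: all adverse events go on the toxicity CRFs |
| 7.3.2 | Reported to the study PI on the local SAE form |
| 13.7.1 | Yes: evaluable from first treatment |

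**2. The scheduled checks.** On infusion days the check precedes the infusion, and the day-1 infusion precedes radiation. So every marked check before follow-up takes place before radiation. The day-1 check can bring out a reaction to the first injection, but the footnote read literally then bars recording it.

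**3. The protocol's own figure.** With n = 6 and a stopping threshold of 2,

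P(stop) = 1 − (1 − p)^6 − 6p(1 − p)^5.

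- p = 1/3: 1 − 0.0878 − 0.2634 = 0.649.
- p = 0.33: 0.642.

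The quoted 65% reproduces. It takes p as the rate of recorded toxicity, so it assumes complete capture.

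**4. Effect of incomplete capture.** Let f be the share of patients with qualifying toxicity whose qualifying events all begin before radiation and go unrecorded. The rate the rule sees is p(1 − f). The protocol gives no value for f, so each row is an assumption, with p = 1/3.

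| Assumed f | Recorded rate | P(stop) |
|---|---|---|
| 0 | 0.333 | 0.649 |
| 10% | 0.300 | 0.580 |
| 25% | 0.250 | 0.466 |
| 33% | 0.222 | 0.399 |
| 50% | 0.167 | 0.263 |

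For example, f = 25% gives 1 − 0.75^6 − 6(0.25)(0.75)^5 = 1 − 0.178 − 0.356 = 0.466.

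**5. Day 3.** Both SRT calendars show an injection on radiation day 3, but no adverse-event assessment is marked that day. This conflicts with the calendars' own footnote that places an assessment before AGuIX on each administration day.

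**The case against.** A reader might infer that reactions to the first injection never reach the CRFs and that the stopping rule cannot see the first exposure. The protocol does not support that. Section 7.6 puts all adverse events on the toxicity CRFs and requires expedited reports to appear there too. Section 7.3.2 covers any event after the initial dose, and the table in 7.3.3 expedites many severe events. The calendars list a Pre-Radiation data-capture timepoint for adverse events, which suggests that the phrase was meant to exclude pre-existing conditions. Toxicity from the first injection that appears after radiation starts is recorded on any reading. All of this stands, and it reduces the point from a proven gap to a contradiction.

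It does not remove the contradiction. The footnote is the more specific instruction, appears in all three calendars and says what is documented on the forms. The 7.3.2 route leads to a study PI who is blinded, whereas the rule is monitored from CRFs by the unblinded coordinator.

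Four further readings should be set aside:

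- **Checks before the infusion hide first-injection reactions.** They do not by themselves: the day-1 check comes after the first injection, and section 10 calls for a toxicity history at each visit. The onset wording does the excluding.
- **The 26% is the expected performance.** It is one assumed case. Section 2.3 reports no significant acute hemodynamic, cardiovascular, renal, hepatic or other toxicities in the phase I study, and section 7.1 ties that study's possibly related serious events to radiotherapy. Both favor a smaller share.
- **A planned between-arm comparison of acute toxicity is truncated.** None is listed in section 1.3 or 13.6.
- **The radiation-necrosis stopping rule is affected.** It concerns resection for necrosis after treatment, so it is not.

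**Conclusion.** The point holds as an internal contradiction with a safety consequence. The onset filter in footnote f/g conflicts with the definition of the whole-cohort acute-toxicity rule and with sections 7.3.2, 7.6 and 13.7.1. A site that follows the calendar would leave off the CRF events that the rule is meant to count; a site that follows 7.6 would not. The protocol does not say which instruction prevails.

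The size depends on an unknown share. The 65% is correct under full capture and drops to about 58% if 10% of qualifying toxicity is lost, and to between 47% and 26% if 25% to 50% is lost. These figures assume a true rate of one third, independent patients, and no rescue of the lost events through another reporting route. The missing day-3 assessment in the SRT calendars is a secondary inconsistency.

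**What to change.** 1. In footnote f (SRS and 6-day calendars) and footnote g (5-day SRT calendar), exclude only toxicities that predate the first AGuIX/placebo injection, in place of those that predate radiation.
2. In section 13.4, state that the whole-cohort rule counts qualifying toxicity from the first injection through 1.5 months after the end of protocol treatment. The present window, "acute, grade 3-5 non-hematologic toxicity within 1.5 months of the end of protocol-based treatment", should say explicitly that events during treatment are included.
3. Reconcile the footnote with 7.3.2, 7.6 and 13.7.1, so that one statement governs what goes on the toxicity CRFs.
4. As a secondary matter, keep the adverse-event check before each infusion and reconcile the two SRT calendars on radiation day 3, where an injection is shown without an assessment.

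The cost is an amendment to the calendar footnotes and section 13.4, plus a change to the CRF onset-date rule. No extra visit is needed, since the injections already take place at scheduled attendances. The sample size and the six-patient threshold are unchanged.

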11. MEASUREMENT OF EFFECT

11.1. Antitumor Effect – Solid Tumors

For the purposes of this study, participants will be re-evaluated for local control at 1.5, 3, 5, 7, and 9 months, and every 3 months thereafter (+/- 4 weeks except 1.5 month visit which is +/- 1 week). Unless noted otherwise, response and progression in this study will be derived from the Response Assessment in Neuro-Oncology (RANO) – Brain Metastasis group.¹ Only radiated lesions will be assessed for response and local control.

11.1.1. Definitions

Evaluable for Target Disease response. Participants will have their response classified according to the definitions stated below.

Evaluable Non-Target Disease Response. Participants who have lesions present at baseline that are evaluable but do not meet the definitions of measurable disease, will be considered evaluable for non-target disease. The response assessment is based on the presence, absence, or unequivocal progression of the lesions.

It is mandated all MRIs include a T1 post sequence with a maximal slice thickness of 1.5mm (e.g. MPRAGE, SPGR, or equivalent) and be amenable to 3D reformatting (standard of care at Brigham and Women's Hospital / Dana-Farber Cancer Institute).

11.1.2. Disease Parameters

Measurable/assessable disease. Measurable lesions are defined as those that can be accurately measured at ≥ 5 mm on at least two dimensions on an MRI.¹ Lesions must be visible on two or more axial slices no more than 1.5mm apart. Gross disease abutting a resected metastasis (cavity) is measurable if the above criteria are met (the surgical cavity itself will not be measured). Dural lesions are measurable if not secondary to disease in underlying bone (i.e. primary dural metastases are measurable). Cystic metastases are measurable if enhancement is present.¹⁶ All tumor measurements must be recorded in millimeters.

Non-measurable/non-assessable disease. All other lesions (or sites of disease), including small lesions (one of longest two diameters <5 mm), are considered non-measurable disease. Bone lesions and leptomeningeal disease are not measurable and are not relevant to this study.

Target lesions. For patients with multiple measurable lesions targeted with radiation on study, between 2-5 measurable lesions in total will be identified as target lesions and recorded and measured at baseline. Target lesions should be selected on the basis of their size (e.g. lesions with the longest diameter) and be representative of the radiated disease, but in addition should be those that lend themselves to reproducible repeated measurements. It may be the case that, on occasion, the largest lesion does not lend itself

to reproducible measurement in which circumstance the next largest lesion which can be measured reproducibly should be selected. Bidimensional measurements will be obtained.

Non-target lesions. All other radiated lesions including any measurable lesions over and above the 5 target lesions should be identified as non-target lesions and should also be recorded at baseline.

11.1.3. Methods for Evaluation of Disease

Metastases will be measured on T1 post MPRAGE or SPGR sequences, or equivalent. MRIs acquired over the course of the study for a given patient must be fused / registered to ensure consistency of evaluation and remove imprecision related to head position / slicing during scan acquisition. Measurements will be made digitally and saved electronically for future reference. All baseline evaluations should be performed as closely as possible to the beginning of treatment as possible.

11.1.4. Response Criteria

11.1.4.1. Evaluation of Target Lesions

Complete Response (CR): Disappearance of all target lesions.

Partial Response (PR): At least a 30% decrease in the sum of the diameters of target lesions, taking as reference the baseline sum diameters.

Progressive Disease (PD): At least a 20% increase in the sum of the diameters of target lesions, taking as reference the smallest size on study (this includes the baseline size if that is the smallest on study). In addition to the relative increase of 20%, at least one lesion must increase by an absolute value of 5 mm or more to be considered progression of the target lesions. Enlargement due to necrosis in the opinion of the study PI does not count as PD.

Stable Disease (SD): Neither sufficient shrinkage to qualify for PR nor sufficient increase to qualify for PD, taking as reference the smallest diameters while on study.

11.1.4.2. Evaluation of Non-Target Lesions

Complete Response (CR): Disappearance of all non-target lesions.

Non-CR/Non-PD: Persistence of one or more non-target lesion(s)

Progressive Disease (PD): *Unequivocal progression* of existing non-target lesions. *Unequivocal progression* should not normally trump target lesion status.

Enlargement due to necrosis in the opinion of the study PI does not count as PD.

Although a clear progression of “non-target” lesions only is exceptional, the opinion of the treating physician and/or study PI should prevail in such circumstances, and the progression status should be confirmed at a later time by the study PI.

11.1.4.3. Evaluation of New Lesions

The finding of a new lesion should be unequivocal (i.e. not due to difference in scanning technique, imaging modality, or findings thought to represent changes other than tumor).

11.1.4.4. Evaluation of Best Overall Response

The best overall response is the best response recorded from the start of the treatment until disease progression/recurrence (taking as reference for progressive disease the smallest measurements recorded since the treatment started). The patient's best response assignment will depend on the achievement of both measurement and confirmation criteria.

For Participants with Measurable Disease (i.e., Target Disease)

Target Lesions	Non-Target Lesions	Overall Response
CR	CR	CR
CR	Non-CR/Non-PD	PR
PR	Non-CR/Non-PD	PR
SD	Non-CR/Non-PD	SD
PD	Any	PD
Any	PD	PD

11.1.5. Local recurrence at the individual metastasis level

Definition of local recurrence: Local recurrence (PD in a radiated metastasis) at the individual metastasis level represents the primary endpoint of the study and will be measured from the date of enrollment to the first date that recurrent or progressive disease is objectively documented (taking as reference for progressive disease the smallest measurements recorded since the treatment started). For lesions ≥ 10 mm in largest unidimensional size at post-radiation nadir, a 20% increase in diameter will constitute a local recurrence. Lesions < 10 mm in maximal unidimensional size prior to PD must display 2-3mm of definitive progression to be considered to have displayed a local recurrence. Metastases that enlarge by $< 20\%$ but which are treated with definitive local

therapy (for example, a metastasis that increases from 21mm to 25mm, at which point a craniotomy is performed) will be right-censored. Enlargement due to radiation necrosis as determined by the Study PI will not count as progression. The study PI (blinded to treatment assignment per the above procedures) will make the delineation of local recurrence versus not.

As a sensitivity analysis, metastases considered to have displayed a local recurrence prompting salvage therapy but not meeting criteria for radiographic PD (for example, a metastasis that increases from 21mm to 25mm, at which point a craniotomy is performed) will be treated as a local recurrence on the date that salvage therapy is initiated.

